7.3. Study monitoring	26
7.4. Inspection / Audit	27
7.5. delegation of tasks	27
7.6. declaration to the competent authorities	27
7.7. Protocol amendments	27
7.8. Computerized data and submission to the CNIL	28
7.9. Patient information	28
7.10. Financing and insurance	28
7.11. Publication rules	29
7.12. Archiving source data	29
8. REFERENCES	30

INTRODUCTION

With advancing age, many patients lose their autonomy. This loss of autonomy can be increased during hospitalization, by the effect of the pathology itself, or by the effect of hospitalization. The aim of the rehabilitation team is to put in place tools to preserve patients' motor skills, through rehabilitation sessions and/or the use of appropriate equipment. In particular, they ensure that walking aids and footwear are adapted to the patient's clinical condition.

However, senior patients arriving on the medical ward do not always have adequate footwear. The teams in charge of these patients, including physiotherapists, are faced with the choice of either keeping the original footwear, or offering patients the option of walking barefoot. The choice of keeping the usual footwear is the most frequent.

For some time now, it has been possible to offer non-slip socks for walking around their wards. However, there is controversy in the scientific literature about the usefulness of these devices. In particular, it is impossible to transpose the results of studies to assess the benefits of these socks for senior citizens.

The aim of this study was to assess the effect of non-slip socks on motor recovery.

1. JUSTIFICATION FOR THE STUDY

1.1. Research positioning

1.1.1. Rational

In 2012, people aged 65 or over represented 17.1% of the population (16% in 2002), half of whom were aged 75 or over. This represents an increase of 45% in 20 years (INSEE, 2012). In 2015, 2.5 million seniors in France were losing their autonomy (INSEE, 2017). Among seniors aged 75 and over, 8.8% live in institutions (INSEE, 2017). The projection for 2050 is that 4 million seniors will lose their autonomy, i.e. 16.4% of all seniors (INSEE, 2017).

Frequently, the aging of sick or frail people undergoes physical deconditioning as a result of pathologies leading to hospitalization. Deconditioning is a psychophysiological process leading to physical inactivity. It is defined as "an amplifier of vulnerability, leading to situations of dependence and an altered quality of life". (Préfaut & Ninot, 2009) . Muscle mass, strength and power decline with age, and by the age of 80, older people have lost half their initial muscle mass (Professional Associations for Physical Activity, Sweden, 2010)

[figure not shown]

Figure 1: The vicious circle of deconditioning from Hadjistavropoulos et al (2011)

According to Hadjistavropoulos et al. (2011) a vicious circle of deconditioning exists in senior citizens. A fall leads to a fear of falling, which leads to activity restriction, which leads to

functional decline, which leads to reduced stability, which leads to an increased risk of falling (**Error! Reference source not found.**).

On arrival on short-stay wards, patients may be tired and/or confused, depending on the reason for their hospitalization. This physical deconditioning may be compounded by a lack of stimulation, which will be an aggravating factor, particularly in the first few days of hospitalization. Physiotherapists will be called in to help.

Physiotherapists will ensure that senior citizens maintain good motor skills. Walking, transferring, moving around their living space and carrying out activities of daily living are essential to maintaining quality of life in the living environment of their choice. (Assessment of motor skills will be developed later). In addition to the intention to move, an important skill for elderly people is motor planning. Motor planning is the necessary step in building the basis of the motor program. The musculoskeletal system's redundancy means that the subject chooses a "typical movement" from among many possible alternatives. This motor planning seems to be impaired in some frail elderly patients (Kubicki & Mourey, 2015).. In this mission to recover motor skills, the physiotherapist must restore patients' ability to walk safely (self-assessment) and securely (physiotherapist's assessment) as soon as possible. To achieve this, and depending on the physiotherapist's assessment, various technical aids are available (Temfemo & Ahmaidi, 2018). These aids include the simple cane, the tripod cane, English canes, walkers with or without wheels etc. The physiotherapist will also need to pay attention to footwear.

In fact, poorly adapted footwear may be experienced as unsafe and/or insecure by the team or the patient. Luk et al. (2015) offered a narrative review of fall prevention in the elderly. They advocate fall prevention interventions such as exercise, environmental modifications, or medication review. These authors also suggest taking an interest in patient footwear. They report on proposals to avoid high heels and use non-slip shoes, based on other studies (McKiernan, 2005; Menant et al., 2008).

The footwear worn by elderly subjects on geriatric wards has also been studied by several teams. Vass et al. (2015) examined and described the type of footwear worn by elderly patients in hospital. They show that many patients wear footwear with insufficient structure to promote optimal stability or gait. Among the various types of footwear, they found non-slip socks for subjects living at home, in an institution or in hospital (Menant et al., 2008; Vass et al., 2015). A recent narrative review looked at the use of anti-slip socks to prevent falls in elderly patients (Hartung & Lalonde, 2017). In their conclusion, the authors do not recommend wearing socks for patients coming from home with limitations on the studies selected. One important limitation is the external validity of the studies, which are partly based on basic research. The other part, from clinical research, is not specifically concerned with our reference population. As a result, it is not possible for us to recommend whether or not non-slip socks should be worn by hospitalized senior patients. However, the question does arise under specific conditions, which we will describe in detail below.

In clinical practice, in the short-stay wards of many hospitals, including CHD-Vendée, patients arrive from the emergency department with either no adapted footwear or no footwear at all. The emergency situation has brought them to hospital without giving them time to pack. In the case of direct hospitalization, a re-evaluation of footwear is also often necessary, in order to adapt footwear to the patient's situation. Other patients, particularly those with major cognitive impairment, who appear to be most at risk, regularly forget their shoes both during the day and at night. All in all, autonomy seems to be impaired by the absence of adapted footwear. When providing care (toileting, dressing, etc.), care assistants will move the patient into his or her chair, rather than having him or her walk to the toilet. In rehabilitation, the practitioner may choose not to take charge of a patient, or to offer partial care to avoid the risks associated with unsuitable footwear. The patient may be asked to walk on his or her own outside the rehabilitation program.

1.1.2. The aim of the study

All in all, we can see that anti-slip socks may be of clinical interest. The scientific literature presents studies with methodological limitations, but above all a different population from the one we are interested in. It is therefore not currently possible to assess the specific benefit of anti-slip socks in an elderly hospitalized population.

Evaluating the benefits of these socks could enable us to recommend them on the basis of solid data. Preventing this iatrogenic loss of autonomy would have a positive impact on patients' motor skills, a quicker and easier return home, and lower healthcare costs.

We'd therefore like to know the benefits of wearing anti-slip socks in the management of these patients, and more specifically on the main objective of rehabilitation in geriatric physiotherapy: motor function.

We believe that wearing non-slip socks improves patients' motor recovery.

1.2. Benefits and risks for research subjects

1.2.1. Benefits

1.2.1.1. *Individual profit*

Improved motor control
Improved practices with the use of non-slip socks

1.2.1.2. *Group profit*

Improved motor care for senior citizens, at a lower cost to society thanks to a shorter length of stay,
Improved motor management for faster discharge

1.2.2. Foreseeable risks and constraints

Constraints :

For both groups, the only constraint added by the research is the specific tests to be taken and the questionnaire to be filled in. Patients will also be asked to use a wheelchair if they leave the hospital ward.

For the experimental group, the additional constraint is the wearing of non-slip socks.

Foreseeable risks :

There is no increased risk associated with wearing anti-slip socks in senior patients.

1.2.3. Benefit/risk balance

This study qualifies as interventional research with minimal risks and constraints, as defined in article L1121-1 of the French Public Health Code. On the basis of all the above-mentioned information, the benefit-risk balance of this study is favorably assessed.

2. OBJECTIVES AND JUDGING CRITERIA

2.1. Objective and primary endpoint

2.1.1. Main objective

Assessing the impact of anti-slip socks on motor recovery in the elderly during hospitalization

2.1.2. Primary endpoint

Evolution of walking speed at the patient's preferred speed over 10m between D1 (start of physiotherapy treatment) and D8. Two tests will be performed at each assessment, and the average of the two tests will be used.

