3.2. Inclusion criteria

- Patient in Geriatric Short Stay or Post-Emergency Medicine,
- Patient aged 75 and over,
- Patient requiring physiotherapy,
- Patient with at least 7 days of physiotherapy treatment
- Patient arrives with unsuitable footwear (assessment at clinician's discretion: no back support, unsuitable size, etc.) or no footwear at all,
- Patient able to walk at least 10 m with or without technical aids,
- Patient with oral consent
- Patient with social security coverage.

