4.6. Identification of all source data not contained in the medical record

1. Confusion Assesment Method scale	at D1
2. Visual Analogue Fatigue Scale	at D1, D1' and D8
3. Type of technical aid(s)	at J1, J1', J8
4. Duration of 10 m walk (2 times) performed	at D1, D1' and D8
5. Duration of double-task 10 m walk (2 times) performed	at D1, D1' and D8
6. Duration of imagined 10 m walk (2 times) performed	at D1, D1' and D8
7. Short-Falls Efficacy Scale International questionnaire	at D1, D1' and D8

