6.2.5. Method for taking into account missing, unused or invalid data

All missing data and their reasons are described for each group.

For the primary endpoint, if data are missing at D8, they will be imputed by the patient's baseline value (D1).

If, for this criterion, more than 10% missing data are observed, a sensitivity analysis of the imputation method will be carried out: a multiple imputation method will be applied.

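### A patient assessed at D8 who cannot complete 10 m has no defined primary outcome, and the natural reading of section 6.2.5 counts that loss of walking as no change

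*Combined protocol and SAP*

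**What the plan says.** Section 2.1.2 defines the primary endpoint as "Evolution of walking speed at the patient's preferred speed over 10m between D1 (start of physiotherapy treatment) and D8", and adds: "Two tests will be performed at each assessment, and the average of the two tests will be used". Section 4.6 gives the source datum for it: "Duration of 10 m walk (2 times) performed". Section 3.2 sets the walking requirement at inclusion: "Patient able to walk at least 10 m with or without technical aids". Section 4.1.5 lists the D8 tests and gives no result for a patient who cannot do them.

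Section 4.7.1 names only withdrawal of consent and death as reasons for ending participation, so a patient who stops walking stays in the study. Section 6.2.7 puts all randomised patients in the main analysis, and section 6.2.1 compares gait speeds by a linear model that takes the D1 value into account.

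The only text on handling is in section 6.2.5. Missing data and their reasons are described by group. For the primary endpoint, "if data are missing at D8, they will be imputed by the patient's baseline value (D1". Then: "If, for this criterion, more than 10% missing data are observed, a sensitivity analysis of the imputation method will be carried out", by multiple imputation. No imputation model is given.

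**The concern.** The introduction and section 1.1 rest the trial on deconditioning and loss of autonomy in hospital, and section 4.1.5 says that D8 is there to assess whether motor ability was preserved or recovered. A patient still on the ward at D8 who can no longer cover 10 m is the clearest motor failure that the trial can observe. The endpoint has no place for that result, because a walk that is not finished has no duration.

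This is not a general objection to carrying the baseline value forward. Here the outcome is known and is the worst possible. A better method for values that nobody observed would still misclassify it.

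At stake is the reading of a positive trial. If more patients lose walking in the sock arm, they enter the superiority test as unchanged, and a gain among the remaining walkers can still carry the result. With 25 patients per arm, a few such patients are enough to matter.

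**Working it through.** **The plan's own figure.** Inputs from section 6.2.2: difference 0.10 m/s, SD 0.10, alpha 5%, power 90%. The normal approximation gives n per arm = 2 × (1.960 + 1.282)² × (0.10/0.10)² = 21.0, so 22 per arm and 44 in all. The two-sample t-test gives 22.02, so 23 per arm and 46 in all, which is the plan's number with a two-sided 5% test. Randomising 50 gives 25 per arm.

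**What one non-walker does.** Under the D1-value rule the change is 0. If inability were scored 0 m/s instead, the arm mean would move by baseline/25:
- baseline 0.4 m/s (assumed): 0.4/25 = 0.016 m/s
- baseline 0.6 m/s (assumed): 0.6/25 = 0.024 m/s
- baseline 0.943 m/s (the literature value for people over 80 in section 4.5.1, not an inpatient figure): 0.943/25 = 0.038 m/s

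That is 16% to 38% of the planned 0.10 m/s per patient. It shows the scale only; 0 m/s is not the scoring recommended here.

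**When the sensitivity analysis runs.** 10% of 50 is 5, and the trigger is more than 10%. Five non-walkers with nothing else missing do not set it off.

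**Expected difference under the D1-value rule.** Assume that walkers change by 0.05 m/s in control and 0.15 m/s with socks, with non-walkers at 0:
- 1 control, 3 sock: (22/25) × 0.15 − (24/25) × 0.05 = 0.132 − 0.048 = 0.084 m/s
- 0 control, 5 sock: (20/25) × 0.15 − 0.05 = 0.120 − 0.050 = 0.070 m/s
- 2 and 2: (23/25) × (0.15 − 0.05) = 0.092 m/s
- 3 control, 1 sock: (24/25) × 0.15 − (22/25) × 0.05 = 0.144 − 0.044 = 0.100 m/s

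**Simulation.** 25 per arm, baseline 0.6 m/s (SD 0.15), SD of change 0.10, the same changes among walkers, linear model on the D1 value, two-sided 5%. The last two columns give the share of trials that declare socks superior:

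| Non-walkers, control / sock | D1-value rule | Worst rank (rank ANCOVA) |
|---|---|---|
| 0 / 0 | about 93% | about 92% |
| 1 / 3 | about 82% | about 63% |
| 0 / 5 | about 65% | about 19% |
| 2 / 2 | about 90% | about 83% |
| 3 / 1 | about 94% | about 94% |

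Two alternatives were also run. Leaving the non-walkers out of the linear model in the 1 / 3 case raises the difference to 0.100 m/s and superiority to about 90%, which favours socks more than the plan does. Entering 0 m/s in the linear model inflates the variance: with 2 per arm, power falls to about 15%.

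**The case against.** The best reply is that section 6.2.5 speaks of missing data and never says that inability is missing. A reader might infer that the plan states this rule for non-walkers. It does not; that is the natural reading, because a test without a duration leaves the field empty. The reply does not rescue the plan, since on the other reading a patient in the intention-to-treat set has no rule at all.

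A reader might also infer that lost walking would be invisible. The documents do not support that. Reasons for missing data are described by group, D8 includes a clinical examination and the type of walking aid, and falls with their consequences are reported. An imbalance could therefore be seen if inability is recorded as a reason. None of this enters the superiority test.

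Nor do the documents show that multiple imputation would give non-walkers the average change of walkers. No model is specified. What can be said is that the analysis is conditional and, as described, assigns inability no score.

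It is tempting to add that the rule would hide a benefit of socks. With 3 non-walkers in control and 1 with socks, the D1-value rule and the worst-rank analysis declare superiority about equally often, so that example changes no decision.

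Finally, the rates are assumed. A split of 3 against 1 in 25 is compatible with chance (Fisher exact p = 0.61), walking aids are allowed, and some decline may appear as a change of aid instead of inability. This stands, and it limits the claim to what could happen.

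**Conclusion.** The point holds. Inability to complete 10 m at D8 is not scored anywhere, and following section 6.2.5 in the natural way enters an observed loss of walking as zero change in the primary analysis. Whether this affects the result depends on how many patients lose walking and in which arm, and the documents give no rate and no inpatient baseline speed.

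Under the assumptions stated above, an excess of non-walkers in the sock arm leaves superiority declared in about 82% (1 and 3) or 65% (0 and 5) of trials, where worst-rank scoring gives about 63% and 19%. The second case triggers no sensitivity analysis if nothing else is missing. The 63% also shows that worst rank tempers the claim without removing it when the imbalance is small.

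The change should be made before any D8 data are reviewed by arm. The study is open, so a scoring rule chosen afterwards would carry little weight.

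**What to change.** 1. In sections 4.1.5 and 4.6, record the D8 10 m test as *completed*, *present but unable to complete*, or *not done (with reason)*.
2. In section 6.2.5, keep every randomised patient in the primary linear model. State that patients unable to complete carry the D1 value there and are not dropped.
3. Add a pre-specified analysis in all randomised patients, run whatever the percentage missing. Patients unable to complete take the worst rank of change (rank ANCOVA on the D1 value), and only tests not done are imputed.
4. Report the number unable to complete in each arm.
5. State that superiority is described as robust only if the worst-rank analysis agrees in direction and significance.

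The cost is one eCRF field, a few sentences in section 6.2.5 and one extra analysis, with no extra patients or visits. The rank analysis gives no effect in m/s. Its power is lower when non-walkers occur, about 83% against 90% with 2 per arm, so a true benefit will sometimes fail the robustness condition.

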2.2. Objectives and secondary endpoints

2.2.1. Secondary objective(s)

1. Assessing the impact of anti-slip socks on short-term motor skills
2. Evaluate the impact of anti-slip socks on motor planning in the short term and during hospitalization
3. Evaluate the impact of wearing socks on dual-task abilities in the short term and during hospitalization
4. Evaluate the evolution of fear of falling with the use of socks in the short term and during hospitalization.
5. Evaluate the impact of socks on the presence of fall(s)
6. Length of stay in geriatric care or post-emergency medicine

2.2.2. Secondary endpoints

1. Change in 10m walking speed between D1 (start of physiotherapy treatment) and D1' ("after a 3-minute walk with the shoe assigned following randomization"),
2. Evolution of isochrony between the speed of walking actually performed and the speed of walking imagined over 10m at D1, D1' and D8. The mean of two tests of each modality will be used.
3. Evolution of isochrony between walking speed and double-task walking speed over 10m at D1,D1' and D8 (Beauchet et al., 2010; Menant et al., 2014). The mean of two tests of each modality will be used.
4. Total score > 10 on the Short-Falls Efficacy Scale International questionnaire at D1, D1' and D8
5. Presence of fall(s) and their consequences during hospitalization
6. Length of stay calculated from start of hospitalization to end of hospitalization

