4. DESIGN AND STUDY PROCESS

4.1. Study schedule

4.1.1. Inclusion and baseline tests (J1)

Patients arrive on the ward and are assessed by the doctor, who prescribes physiotherapy if necessary.

The physiotherapist takes note of the prescription on the first working day thereafter. The physiotherapist carries out a routine analysis of the patient's footwear. If the footwear is unsuitable, or if the patient is barefoot, the physiotherapist checks the patient's eligibility criteria. If the patient meets these criteria, he or she is informed of the study. If the patient gives oral consent, the physiotherapist will perform the Baseline tests (D1).

Baseline: J1 tests

The physiotherapist assesses the patient during the first diagnostic session, and performs the *Confusion Assessment Method* if it has not been done in routine practice.

A Visual Analogue Fatigue Assessment will be carried out prior to clinical testing.

For research purposes, the J1 tests will be performed barefoot:

1. Patient's walking speed over 10 m (2 times)
2. Walking speed in dual-task situation over 10 m (2 times)

Two other less common but validated assessments in this population will be carried out.

3. Imagined walking speed over 10 m (2 times)

The average of each of the two tests will be used for items 1 to 4.

Together, these tests take the patient around 10 minutes.

4. Short-Falls Efficacy Scale International Questionnaire

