4.1.3. J1' follow-up

After these 3 minutes of walking with or without the socks, depending on the randomization arm, and in order to assess the immediate effect of wearing anti-slip socks on motor skills, the patient will perform the same tests as on D1, in the same order.

A Visual Analogue Fatigue Assessment will be performed prior to the following clinical tests:

1. Patient's walking speed over 10 m (2 times)
2. Walking speed in dual-task situation over 10 m (2 times)
3. Imagined walking speed over 10 m (2 times)

The tests will be carried out by the patient with bare feet (control arm) or with non-slip socks (experimental arm).

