4.1.5. Follow-up J8

At D8, in order to assess the effect of socks on motor preservation/recovery, the patient will be reassessed under the same conditions as at D1, i.e. barefoot, using the same tests as at D1 and in the same order.

A Visual Analogue Fatigue Assessment will be performed prior to the following clinical tests:

1. Patient's walking speed over 10 m (2 times)
2. Walking speed in dual-task situation over 10 m (2 times)
3. Imagined walking speed over 10 m (2 times)
4. Short-Falls Efficacy Scale International Questionnaire

Study schedule

Actions	J1	J1' (after 3 minutes of free walking)	J8	Hospital discharge
Patient information	X			
Informed Consent	X			
Checking inclusion and non-inclusion criteria	X			
Randomization	X			
Confusion Assessment Method	X			
EVA fatigue	X	X	X	
History (falls, MMSE, etc.)	X			
Type of technical aid	X	X	X	
Clinical examination	X		X	
Tests :				
• Walking speed at patient's preferred speed over 10m (x2),				
• Double-task walking speed over 10m (x2),	X	X	X	
• Imagined walking speed over 10m (x2),				
Short-FESI questionnaire	X		X	
Length of stay in geriatric care or post-emergency medicine				X

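### The plan contradicts itself on whether the Short-FES-I is collected at D1'; if the D1' visit list and schedule are followed, the planned D1' Chi2 test has no data

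*Combined protocol and SAP*

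**What the plan says.** Four places in the combined protocol and SAP call for a Short-FES-I score at D1', the assessment made after the 3-minute walk in the assigned condition:

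- Secondary objective 4 (2.2.1): "Evaluate the evolution of fear of falling with the use of socks in the short term and during hospitalization". D1' is the only short-term assessment in the plan.
- Secondary endpoint 4 (2.2.2): "Total score > 10 on the Short-Falls Efficacy Scale International questionnaire at D1, D1' and D8".
- The source-data list (4.6, item 7), which gives D1, D1' and D8 for this questionnaire.
- The statistical methods (6.2.1), which plan a Chi2 test of the proportion with fear of falling at D1' and at D8.

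Two places leave it out. The D1' visit list (4.1.3) ends at "3. Imagined walking speed over 10 m (2 times". In the schedule at the end of 4.1.5, the row "Short-FESI questionnaire" has an X at J1 and at J8 and an empty J1' cell.

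The sentence that introduces the 4.1.3 list adds to the difficulty. It says that "the patient will perform the same tests as on D1, in the same order". The D1 battery in 4.1.1 opens with "For research purposes, the J1 tests will be performed barefoot" and ends with "4. Short-Falls Efficacy Scale International Questionnaire".

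**The concern.** The sections that define the endpoint and its analysis assume a measurement that the sections describing the visit do not ask for. The visit list and the schedule are what staff are most likely to have in hand when they see the patient. If they work from these, the questionnaire is not given at D1', and a prespecified test has nothing to analyse. If some staff rely instead on the general sentence in 4.1.3 or on 4.6, collection would be partial, and whether a score exists would depend on who ran the visit. In neither case can the gap be filled afterwards, because the score describes the patient at that session.

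**Working it through.** No figure in the plan has to be reproduced for this point. The check is to set side by side every section that fixes when the Short-FES-I is collected or used.

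| Section | D1 | D1' | D8 |
|---|---|---|---|
| 2.2.1, objective 4 | – | needed (short term) | needed (during hospitalization) |
| 2.2.2, endpoint 4 | yes | yes | yes |
| 4.6, item 7 | yes | yes | yes |
| 6.2.1, Chi2 test | – | yes | yes |
| 4.1.1, D1 list | yes (item 4) | – | – |
| 4.1.3, D1' list | – | **no** (ends at item 3) | – |
| 4.1.5, D8 list | – | – | yes (item 4) |
| Schedule | yes | **no** (empty cell) | yes |

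D1 and D8 agree throughout. Only D1' is in dispute.

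**Is the empty cell a PDF artefact?** It is unlikely. The fatigue scale, technical aid and walking-test rows of the same table all show their J1' mark, and the 4.1.3 list omits the questionnaire independently. Comparing 4.6 with the schedule isolates the problem: items 1 to 6 (Confusion Assessment Method, fatigue scale, technical aid and the three timed walks) agree on timing, and only item 7 does not.

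**Does the general sentence in 4.1.3 settle it?** It does not. For D8, 4.1.5 uses nearly the same phrase, "using the same tests as at D1 and in the same order", and then lists four items including the questionnaire. In 4.1.3 the phrase is followed by three items without it. If the D1 battery includes the questionnaire, 4.1.3 conflicts with itself. If it does not, 4.1.3 conflicts more firmly with 2.2.1, 2.2.2, 4.6 and 6.2.1.

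**Counts**, with 50 patients randomized (6.2.2):

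- Questionnaires under 2.2.2 and 4.6: 3 × 50 = 150.
- Questionnaires under the visit lists and the schedule: 2 × 50 = 100.
- Difference: 150 − 100 = 50, all at D1'.
- Fear-of-falling Chi2 comparisons planned in 6.2.1: 2 (D1' and D8). With data if the visit list and schedule are followed: 1.

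**The case against.** The strongest reply is that the questionnaire was never one of the tests. In 4.1.1 the sentence on how long the tests take comes before the questionnaire. The schedule gives it a row outside the block of tests, and 1.2.2 names tests and questionnaire separately. On that reading 4.1.3 is consistent with itself, and the visit list and schedule may record a deliberate choice that was never carried into the other sections. This has some force. The layout of 4.1.1 is ambiguous, and the documents do not prove which version was intended. Against it, 4.1.1 numbers the questionnaire as item 4 and refers to items 1 to 4 together, and 4.1.5 includes it in a four-item list introduced as the D1 tests. The balance favours collection at D1'. In any case this reading does not remove the main contradiction, because the endpoint, the source-data list and the analysis still name D1'.

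A second reply is that the data would be captured anyway. Section 4.6 is itself an operational list that names D1', and 6.1.1 requires the eCRF to hold everything the analysis needs. That is a partial safeguard only: the eCRF is not shown, and it would be built from a protocol that gives two answers. What stands is that a total loss is the worst case and not a forecast.

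**Conclusion.** The concern holds. The plan gives two incompatible answers on whether the Short-FES-I is collected at D1', and nothing in it resolves them. At the extremes, D1' scores number 50 or 0. At 0, one of the two fear-of-falling Chi2 comparisons cannot be run, and the short-term part of objective 4 is lost. The count of 50 assumes that every randomized patient completes D1'. The count of 0 assumes that staff follow the 4.1.3 list and the schedule and that the eCRF does not prompt for the questionnaire. The documents do not show how likely that is.

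The damage is confined to one time point of one secondary endpoint. The primary endpoint, the sample size and the D8 fear-of-falling comparison do not depend on it. The plan should be corrected, but the contradiction does not threaten the main conclusion of the trial.

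**What to change.** The sponsor should state which was intended and bring the sections into line.

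- **Option 1, collect at D1'.** Add the Short-FES-I as item 4 of the list in 4.1.3 and put an X in the J1' column of the schedule. This keeps objective 4 as stated and fits the weight of the text. It costs two edits and one more 7-item self-questionnaire per patient, 50 in all. The documents do not give its completion time.
- **Option 2, do not collect at D1'.** Remove D1' from endpoint 4 in 2.2.2, item 7 in 4.6 and the Chi2 test in 6.2.1; drop the short-term part of objective 4 in 2.2.1; and reword 4.1.3 to refer to the walking tests only, without the questionnaire. This costs five wording edits and gives up the short-term fear-of-falling question. The 4.1.3 edit is needed because 4.1.1 lists the questionnaire among the D1 tests.

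Under either option, check that the eCRF form for D1' matches the choice.
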